9. RESEARCH METHODS

9.1. Study design

This is a prospective, observational, multi-center, non-interventional PASS conducted to evaluate safety of study participants receiving the Pfizer-BioNTech COVID-19 mRNA vaccine using a combination of primary data collection and secondary data analysis. This study will not provide or make recommendations on any vaccine use. Participants will be invited to enroll and consented in the study after the decision has been made to administer the vaccine, and participation in this study will not change or influence a participant's standard of care in any way. There are no protocol-mandated visits or procedures associated with the study. The study period is 30 months. Each participant will be followed from baseline (vaccination dose received at index date, where index date is defined as the date of Pfizer-BioNTech COVID-19 mRNA vaccine dose received within the 5 days prior to enrolment, regardless of dose number) until death, withdrawal of consent, loss to follow-up, 24 months or end of study period, whichever occurs first.

Data will be collected at baseline directly from the participants receiving the vaccine and/or their designee; this may include a health care provider (HCP) or study staff at the site administering the vaccine. Follow-up data on medically attended safety events of interest will be collected directly from persons receiving the vaccine.

[figure not shown]
This study will collect information on all reported occurrences of the medically attended safety events of interest, which is based on the AESI lists specified by ACCESSS and SPEAC/Brighton Collaboration, for which the participant sought medical care during the study period. Participants will choose their preferred method for submitting follow-up data:

- Completing questionnaires via a participant portal within the study website or mobile app, or
- Telephone interview via outbound calls from the IQVIA call center.

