9.2.1. Inclusion criteria

Participants must meet all of the following inclusion criteria to be eligible for inclusion in the study:

1. Participant's age is 18 years and above, and in accordance with the approved product label of the country where the study is conducted.
2. Enrolment within 5 days of receipt of any dose (i.e. first, second, or any subsequent booster dose) of the Pfizer-BioNTech COVID-19 mRNA vaccine.

Note:

Heterologous primary vaccination (two different COVID-19 vaccines [different manufacturers] received for the first and second doses of a primary [initial] course) and heterologous boosting (a third dose of a different manufacturers COVID-19 vaccine as a booster 3 to 6 months after a primary vaccination course) are now commonplace.

Individuals receiving heterologous booster doses are allowed to enroll in this study, if the booster dose received is the Pfizer-BioNTech COVID-19 mRNA vaccine. However, if a participant is enrolling at second Pfizer-BioNTech COVID-19 mRNA vaccine dose, the first dose received must have also been the Pfizer-BioNTech COVID-19 mRNA vaccine². If a participant is enrolling at second or booster dose of Pfizer-BioNTech COVID-19 mRNA vaccine, the participant must be able to provide the date and manufacturer of all previous COVID-19 vaccine doses received in order to be eligible for inclusion.

3. Adult participants willing to provide informed consent according to local regulations and complete all study procedures in accordance with the protocol, including consent for the study team to contact the treating HCP or healthcare facility to obtain additional information related to safety events reported by the participant.

² Including patients receiving the Pfizer-BioNTech COVID-19 mRNA vaccine as their second dose, who have not received the Pfizer-BioNTech COVID-19 mRNA vaccine as their first dose, would result in any vaccine effects being difficult to distinguish between manufacturers. No such restrictions are placed upon participants enrolling at booster doses, as the time window between doses is anticipated to be longer, with reduced likelihood of overlapping risk intervals.

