9.3.1. Safety Outcome Definitions

Data on medically attended safety events of interest will be collected from the time of participants' enrolment into the study until death, withdrawal of consent, loss to follow-up or end of study period, whichever occurs first.

Medically attended safety events of interest in this study are listed in Table 2. These events are based on the AESI lists developed by ACCESS and SPEAC/Brighton Collaboration, which consists of events previously identified with immunization in general (e.g. anaphylaxis, GBS), with vaccine platforms relevant to COVID-19 vaccine development, or with theoretical concerns based on immunopathogenesis or viral replication during wild type disease (4, 5).

Participant reported medically attended safety events of interest will be followed up with the treating HCPs or through medical record documentation if needed to validate or establish the diagnosis associated with the event and validate the occurrence of a safety event of interest, or other clinically significant event. Additional safety events may be added as endpoints based on emerging findings from clinical studies, spontaneous reports, literature or updates in guidance.

Table 2. Medically attended safety events of interest^a

Body System	Safety Event
Neurologic	Generalized convulsion/ seizure
	Guillain-Barré Syndrome (GBS)
	Aseptic meningitis
	Encephalitis / Encephalomyelitis
	Other acute demyelinating diseases
	Transverse myelitis
	Multiple sclerosis
	Optic neuritis

090177e1991e3913\Approved\Approved On: 18-Jan-2022 22:29 (GMT)

Table 2. Medically attended safety events of interest^a

Body System	Safety Event
	Bell's palsy
	Acute disseminated encephalomyelitis
Immunologic	Anaphylaxis
	Vasculitides*
	Arthritis and arthralgia
	Multisystem inflammatory syndrome in adults (MIS-A)
	Kawasaki disease
	Fibromyalgia
	Autoimmune thyroiditis
COVID-19	Severe COVID-19 disease * **
	Acute respiratory distress syndrome
	Microangiopathy*
	Heart failure and cardiogenic shock*
	Stress cardiomyopathy*
	Coronary artery disease*
	Arrhythmia*
	Deep vein thrombosis
	Pulmonary embolus
	Cerebrovascular stroke
	Limb ischemia*
	Hemorrhagic disease*
	Acute kidney injury*
	Acute liver injury
	Chilblain-like lesions
	Single organ cutaneous vasculitis*
	Erythema multiforme*
	Anosmia, Ageusia
	Acute pancreatitis

090177e1991e3913\Approved\Approved On: 18-Jan-2022 22:29 (GMT)

Table 2. Medically attended safety events of interest^a

Body System	Safety Event
	Rhabdomyolysis

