9.7. Data analysis

The study population of Pfizer-BioNTech COVID-19 mRNA vaccine recipients will be described in terms of demographic characteristics (age, gender, ethnicity, occupation) and medical history characteristics outlined in [Section 9.4.1](#). Vaccination characteristics, including number of doses received and interval between doses, will also be described.

The incidence rates of medically attended safety events of interest and corresponding 95% Poisson exact confidence intervals (95% CI) will be estimated in the primary safety dataset of participants who enroll within 2 days of vaccination. Rates will also be estimated for the overall study population and within subcohorts of interest such as pregnant vaccine recipients, immunocompromised participants, and within age-categories.

A final analysis will also be conducted for the following subcohorts of interest, given the potential for mixed exposure:

1. **Pfizer-BioNTech vaccine only**: all participants who only receive Pfizer-BioNTech COVID-19 mRNA vaccine(s), and no other COVID-19 vaccine(s), prior to index date and during their follow-up period.
2. **Heterologous vaccination**:
 - a) **Pfizer-BioNTech booster(s) only**: all participants who received only Pfizer-BioNTech COVID-19 mRNA vaccine dose(s) as booster dose(s) during the study period, but where the primary vaccine course (prior to index date) was non-Pfizer-BioNTech.
 - b) **Heterologous primary course**: all participants who received Pfizer-BioNTech COVID-19 mRNA vaccine as a first dose at index date, and then received a non-Pfizer-BioNTech second dose during their follow-up period. No booster doses were received.
 - c) **Other combination heterologous vaccine course/booster**: all participants with a heterologous primary course and/or heterologous booster dose(s), who do not fit the criteria for inclusion in subcohorts 2(a)-(b) above.

It is anticipated that rates will be reported for the following intervals, overall and for each of the subcohorts of interest:

- Follow-up at weeks 1, 2, 4, 6 and 8 following a Pfizer-BioNTech COVID-19 mRNA vaccine dose,
- Quarterly follow-up following a Pfizer-BioNTech COVID-19 mRNA vaccine dose (until 24 months following index date vaccine dose, or end of study, whichever occurs first).

[figure not shown]

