Time at risk will be assessed from the Pfizer-BioNTech COVID-19 mRNA vaccine dose until the subsequent follow-up time point or until the next Pfizer-BioNTech COVID-19 mRNA vaccine dose received, death, withdrawal of consent, loss to follow-up, 24 months or end of study period, whichever occurs first. Sensitivity analysis may be conducted with censoring at any COVID-19 vaccine dose received.

All cases of reported laboratory confirmed COVID-19 in the study population will be described by the Brighton Collaboration “Vaccine-associated Enhanced Disease” Working Group case definitions for COVID-19 VAED.

Counts of newly reported medically attended safety events of interest and counts of vaccinated participants will be summarized as per the intervals above. Counts will be summarized by whether medical validation of the event was possible, or not.

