9.9. Limitations of the research methods

This is a non-interventional, multinational, multi-center PASS to further document the safety profile of participants vaccinated with the Pfizer-BioNTech COVID-19 mRNA vaccine. Participants will be followed for up to 24 months after their vaccine dose.

The time frame of 24 months post-vaccination will allow evaluation of the long-term safety profile of the Pfizer-BioNTech COVID-19 mRNA vaccine in a real-world population. To reduce the likelihood of sampling bias, broad inclusion criteria and consecutive participant selection will be applied.

Recruiting participants soon after vaccination is important to prevent over-representation of participants who elect to enroll only after experiencing an event. The study recruitment strategy will encourage enrolment within 2 days of vaccination, but in consideration of the enrolment goal of up to 10,000 participants, diverse and changing local vaccine roll-out strategies, and to provide potential participants enough time to inform themselves fully before consenting, only enrollment within 5 days of vaccination will be eligible.

There is potential for loss to follow-up prior to study completion. To reduce the likelihood of loss to follow-up, active monitoring of participants will be employed. For participants who discontinue the study prematurely, the reason(s) for discontinuation will be recorded. The sponsor will aim to minimize missing information by the measures outlined in [Section 9.7.1](#).

There is also the potential for recall bias where participants may not remember or report events that occurred in between the questionnaire intervals. This is likely to be minimized by focusing on serious events and hospitalizations.

As participants may receive multiple vaccine doses during the study period, and may receive different types of COVID-19 vaccine, attributing outcomes to the relevant exposure period may be challenging. However, this will be mitigated through the collection of data on other vaccines (including date and manufacturer), including those received prior to the index date dose (e.g. to facilitate exclusion of participants who received the Pfizer-BioNTech COVID-19 mRNA vaccine as their second dose, who *did not* receive the same vaccine as their first dose), as well as through sensitivity analysis.

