18.1.2. Each subsequent COVID-19 vaccine dose questionnaire

- Vaccination information:
 - Manufacturer
 - Date of vaccination
- Pregnancy status (female participants of childbearing potential only)

⁶ https://www.bgs.org.uk/sites/default/files/content/resources/files/2018-05-23/fff_full.pdf

- Any changes in contact information
- Any changes in preferred participant follow-up method

The following additional fields completed if the vaccine received is the Pfizer-BioNTech COVID-19 mRNA vaccine:

- Additional vaccination information:
 - Location (i.e. vaccination center)
 - Vaccine lot number
 - Anatomical site where vaccine was administered
- Any changes in prior submitted medical history
 - Any concomitant medication taken within 7 days prior to vaccination (*Drugbank coded*)
 - Any other vaccinations (other than the COVID-19 vaccine, and other than any previously reported) in the last 6 months
 - Presence of potential active viral disease within previous 3 days prior to vaccination (e.g. fever, symptoms of cold, flu, or other inflammatory/infectious process)

18.1.3. Safety outcome follow-up questionnaire (weekly, monthly, and long-term follow-up, through 24 months following the index date vaccine dose)

In addition to discontinuation data being collected during follow up (discontinuation date, number of vaccine doses received by discontinuation, and discontinuation reason), outcome follow up will include:

- Pregnancy status (female participants of childbearing potential only)
- Have you received any non-routine (unplanned) medical care since your vaccination / last follow-up questionnaire? (*with the below options to be tailored for each country*)
 - Yes – primary care physician / general practitioner
 - Yes – emergency department
 - Yes – hospital (inpatient)
 - Yes – hospital (outpatient)
 - Yes – Intensive Care Unit or High Dependency Unit
 - No

If a participant selects yes to any of the above, they will be asked how many events they need to report, and asked to complete all of the following questions for each event:

- What was the main purpose of your non-routine (unplanned) medical care?
 - I have been diagnosed with this condition in the past, but my symptoms changed or got worse
 - I experienced new symptoms and was diagnosed with this condition for the first time
- Relevant details will be collected:
 - Date of visit
 - Date of end of visit (if applicable)

- Details of HCP (as minimum: name, location, email)

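### For the index dose, time at risk, event collection and the first questionnaire start at different points, so early rates lack a matched numerator and denominator

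*Protocol*

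**What the plan says.** Section 9.7 sets the person-time rule for the incidence rates: "Time at risk will be assessed from the Pfizer-BioNTech COVID-19 mRNA vaccine dose until the subsequent follow-up time point", or to an earlier censoring event. For the index dose the clock therefore starts on the day of vaccination, in line with 9.1, which follows each participant from the index-date dose.

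Section 9.3.1 sets a different start for the numerator. Data on safety events "will be collected from the time of participants' enrolment into the study until death, withdrawal of consent, loss to follow-up or end of study period".

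The follow-up questionnaire in Annex 3 (18.1.3) sets a third rule. It asks: "Have you received any non-routine (unplanned) medical care since your vaccination / last follow-up questionnaire". At the first follow-up that reaches back to the dose.

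The gap between dose and enrolment is bounded in two places. Section 9.2.1 requires "Enrolment within 5 days of receipt of any dose (i.e. first, second, or any subsequent booster dose", and 9.7 says that incidence rates "will be estimated in the primary safety dataset of participants who enroll within 2 days of vaccination". Rates are also to be given for the overall study population and for subcohorts. Under 9.2.3 the invitation follows vaccination, and under 9.2 a person counts as enrolled only after consenting and reporting the vaccination date.

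Section 9.9 recognises one consequence: "Recruiting participants soon after vaccination is important to prevent over-representation of participants who elect to enroll only after experiencing an event". Section 9.7 gives no delayed-entry rule and no rule for events dated between dose and enrolment.

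**The concern.** A rate is interpretable only when its numerator and denominator cover the same days in the same people. For the index dose the protocol does not ensure this, and the direction of the error depends on which passage the analyst follows.

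- **If 9.3.1 governs,** the days between dose and enrolment add person-time but cannot add events. Early rates are then too low.
- **If Annex 3 governs,** events from those days are counted by recall, but only from people who later enrolled. Rates rise if an event prompts someone to enrol, and fall if it keeps them from enrolling.
- **On either reading,** nobody who died between dose and enrolment can be in the cohort. Death is a listed safety event (Table 2) and a candidate for SCRI analysis (Annex 4), so for that outcome the gap is immortal time.

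The error falls in the first days after vaccination. Section 9.7 reports week-1 rates overall and by subcohort. Reactogenicity is collected only in week 1 (9.4.2). Anaphylaxis is listed for SCRI in Annex 4. If the start point is chosen after early counts have been seen, the direction of bias is in effect chosen too.

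**Working it through.** **The plan's own figure.** The enrolment target in 9.2 and 9.5 is 10,000/(1 − 0.25) = 13,333.3, rounded up to 13,334. This agrees. The protocol gives no figure for person-time between dose and enrolment.

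**Inputs.** The maximum gap *g* is 2 days in the primary safety dataset (9.7) and 5 days overall (9.2.1). The shortest reporting interval *L* is week 1, or 7 days (9.7). The distribution of *g* is not given, so the maximum is shown together with an assumed mean of half the maximum.

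**Formulas, if pre-enrolment events are not counted.** Share of interval person-time with no countable event = *g/L*. Under a constant hazard within the interval, the true rate is the reported rate times *L*/(*L* − *g*).

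| Week 1 (*L* = 7) | Share | Factor |
|---|---|---|
| Primary, all enrol on day 2 | 2/7 = 28.6% | 7/5 = 1.40 |
| Primary, mean gap 1 day (assumed) | 1/7 = 14.3% | 7/6 = 1.17 |
| Overall, all enrol on day 5 | 5/7 = 71.4% | 7/2 = 3.50 |
| Overall, mean gap 2.5 days (assumed) | 2.5/7 = 35.7% | 7/4.5 = 1.56 |

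**How fast it fades (maximum shares).**
- First 12 weeks (84 days): 2/84 = 2.4% primary; 5/84 = 6.0% overall.
- 24 months (730 days): 2/730 = 0.27% primary; 5/730 = 0.68% overall.

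**The same in person-years.** If dropouts contribute one year each (an assumption), total follow-up is 13,334 × (0.75 × 2 + 0.25 × 1) = 23,334.5 person-years. With exact Poisson limits this base reproduces the 25% attrition rows of Table 4 for the two highest rates: [2436, 2565] at 2500 and [4910, 5092] at 5000 per 10,000 person-years. Time before enrolment is then at most 13,334 × 5/365.25 = 182.5 person-years (0.78%). If all 13,334 enrolled within 2 days it would be at most 13,334 × 2/365.25 = 73.0 (0.31%).

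**OE and SCRI.** The OE expected count is a background rate times person-time, so unobserved days inflate it by the same factor. Taking a 7-day window purely as an illustration, the OE ratio would be multiplied by 5/7 = 0.71 (2-day gap) or 2/7 = 0.29 (5-day gap) at worst. An SCRI rate ratio with a 7-day risk interval shrinks in the same way if the offset keeps the unobserved days. Actual windows are left to the SAP, so the effect on the real windows cannot be sized here.

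**If pre-enrolment events are counted by recall.** No arithmetic is possible: the bias depends on how strongly an early event changes the chance of enrolling, and the protocol gives no figure for that.

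**The case against.** The strongest reply is that the dose is the intended origin throughout. Section 9.1 follows participants from the index-date dose, 9.7 starts time at risk there, and the questionnaire reaches back to vaccination. On that view 9.3.1 only says when data gathering begins, since consent must precede any data collection (9.4). This has force. A reader might infer that events are collected solely from enrolment, making all the early time empty; the documents do not support that, because Annex 3 can capture earlier events. But this reading leaves the selection problem and the immortal time for death in place, and 9.3.1 still says otherwise.

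A second reply is that the design already limits the damage, and it does. The primary dataset is capped at 2 days, recruitment encourages enrolment within 2 days (9.2.3), and the abstract describes enrolment at presentation for vaccination. A reader might apply the 71% to the primary analysis; it belongs only to the overall population, and only if everyone enrolled on day 5. Later Pfizer-BioNTech doses fall within observed follow-up, so week-1 rates that pool doses are diluted.

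A third reply concerns the remedy. A reader might conclude that delayed entry must replace the dose as origin. That would remove immediate index-dose reactions, such as anaphylaxis, from rates, OE and SCRI. It would also need an onset date, and Annex 3 lists only visit dates. This objection stands: delayed entry is better as a prespecified companion analysis.

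Detail may properly be left to the SAP, which is not at hand. But the protocol has itself fixed the person-time rule and the collection start, inconsistently, and 9.7 says that major changes to primary endpoint definitions or their analyses call for a protocol amendment.

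**Conclusion.** The point holds in limited form. For the index dose, 9.3.1 conflicts with both 9.7 and Annex 3 on when event counting starts, and nothing in the protocol resolves it.

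Under 9.3.1, index-dose week-1 rates are understated: days with no countable event take up at most 29% of person-time in the primary dataset and 71% overall. These are worst cases, assuming constant hazard and enrolment on the last permitted day; with a mean gap of half the maximum they are about 14% and 36%. Under Annex 3 the bias is one of selection, of unknown size and either direction. For death the gap is immortal time on both readings.

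A reader might take this as undermining the 24-month incidence rates. It does not: the person-time at issue is below 1% of follow-up on every assumption shown. The consequence is confined to early intervals and short OE or SCRI windows after the index dose.

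**What to change.** 1. Reconcile 9.3.1, 9.7 and Annex 3 to one stated start of event counting for the index dose, so that numerators, denominators, OE expected counts and SCRI offsets cover the same days.
2. If the dose is kept as origin, say that recalled events count. Flag those dated between dose and enrolment by the reported or provider-confirmed visit date, and report them separately as counts.
3. Prespecify, for the index dose and the early intervals, an analysis that starts time at risk at enrolment (delayed entry, with the time scale still measured from the dose) and drops both events and person-time before enrolment.
4. Start person-time for death at enrolment in all analyses.
5. Leave the start at the dose for later Pfizer-BioNTech doses received while under follow-up.

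The cost is a short amendment, one flag and one extra analysis. Dose and enrolment dates are already needed to apply the 2-day and 5-day limits, so no new data are required. One limit remains: when enrolment and event fall on the same day, dates alone cannot show which came first, and the rule should say how such events are classed. The change is best made before further week-1 results are tabulated.
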